Our study will enroll participants with at least two fingernails involved. This will allow us to use placebo in one fingernail of every participant, thus establishing the efficacy of ITA in our study by allowing us to compare placebo to ITA. In addition to efficacy assessments, we will measure changes in quality of life due to the study intervention as an outcome. Quality of life assessments will be done with the NPQ10 assessment, which is a validated assessment tool developed to measure quality of life in nail psoriasis.[14] This tool is included in Appendix B.

All fingernails not treated with placebo will undergo randomization to four groups corresponding to four concentrations of ITA under investigation (2.5, 5.0, 7.5, 10.0 mg/mL). Thus, a participant with five affected fingernails may have a different concentration of ITA used as the study intervention in each fingernail. This approach has been used in studies of ITA in other dermatologic diseases such as alopecia areata. [15] In the cited study, the lesions of subjects with alopecia areata were divided into four quadrants, corresponding to four concentrations of ITA that were injected. We believe this approach will be helpful in comparing the efficacy of different concentrations in the same patient.

SIGNIFICANCE

Psoriasis is a chronic, inflammatory condition that affects millions of people in the United States. Approximately 50% of patients with cutaneous psoriasis have nail involvement; nail psoriasis causes significant pain, and can lead to loss of manual dexterity, therefore impairing the ability to use the hands or perform work. Intralesional triamcinolone acetonide is considered one of the mainstays of treatment for nail psoriasis. By determining the lowest effective concentration of this medication for nail psoriasis, we can minimize side effects for millions of people affected with nail psoriasis worldwide.

OBJECTIVES

The primary objective of this study is to determine the lowest effective concentration of intralesional triamcinolone acetonide in the treatment of nail psoriasis.

The secondary objective is to determine that intralesional triamcinolone acetonide is effective in the treatment of nail psoriasis when compared to placebo, using the Nail Psoriasis Severity Index as a measure of improvement.

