All concomitant medication usage from the period of 60 days prior to the trial through the trial period shall be documented and include the following information:

1. Medication
2. Indication
3. Dosage (including frequency)
4. Start / Stop date

All concomitant medication usage will be checked with respect to exclusion criteria and cross-referenced to adverse events (if any).

RESEARCH DESIGN / METHODS

Our approach is to assess the efficacy and safety of different concentrations of ITA in the treatment of nail psoriasis. A similar approach has been taken with psoriasis of the skin, and alopecia areata.[15, 16]

Hypothesis: The lowest concentration of ITA tested offers the best ratio of efficacy to safety.

Study Design: A total of 10 subjects who have nail psoriasis of at least two fingernails will be enrolled. During the screening visit, the investigator will discuss with each subject the nature of the study, its requirements and its restrictions during the Informed Consent Process.

The following will be performed at the screening visit:

- Review of inclusion/exclusion criteria
- Medical history and demographics including age, gender, history of psoriasis
- Review of medications
- Examination of the fingernails
- Possible tissue sampling (clipping the nail) to rule out onychomycosis
- X-ray of the affected hand
- Administration of a survey assessing quality of life at baseline.
- Use the study intervention (intralesional triamcinolone acetonide injections) on your fingernail(s)

Eliciting the patient history and physical exam are part of standard clinical practice.

Nail psoriasis is a clinical diagnosis. Tissue sampling may be taken if there is a question about diagnosis, or if there is a possible confounding diagnosis such as onychomycosis. X-rays of the hand may also be taken to determine if there is co-existing arthritic involvement, which is very common in nail psoriasis. Both of these events are part of standard clinical practice and are not research-related procedures. Patients who only decline to obtain x-rays won't be excluded from the study.

After completion of the informed consent process, the study site will take photos of the affected fingernails proposed for enrollment.

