Skin atrophy	0 = none 1 2 3 = extreme
Bleeding	0 = none 1 2 3 = extreme
Burning/cold sensation	0 = none 1 2 3 = extreme
Hematoma	0 = none 1 2 3 = extreme

Other (please describe and grade, or enter '0' for none)	
--	--

Table 1. The physician shall evaluate the patient's response to the treatment and screen for possible side effects as listed. 0 = none, 1 = mild, 2 = moderate and 3 = extreme.

Photos shall be taken of any visible treatment effects.

EFFICACY EVALUATIONS

The primary endpoint of this study is to assess the lowest effective concentration of intralesional triamcinolone acetonide in the treatment of nail psoriasis. Safety and tolerability shall be determined based on the reported number of adverse events as outlined in the Adverse Events Section and subject-reported symptoms (if any).

In order to evaluate the efficacy of the proposed treatment, high quality photographs will be taken before and after treatment using standardized lighting, exposure settings, and subject positioning. Trained individuals shall assess the changes in the photographs as outlined in the following paragraphs.

Preliminary assessment of the efficacy of the study intervention will be determined by measuring the amount of clear nail growth. This growth will be compared to the initial amount of clear nail recorded at baseline. Changes in clear area and NaPSI will also be reviewed as study intervention progresses and compared to baseline values.

INSTITUTIONAL REVIEW BOARD

Prior to beginning this study, approval for all study related documents (protocol, consent form, advertising) will be obtained from the Weill Cornell Medical College IRB.

DATA ANALYSIS

Efficacy will be evaluated using nail plate measurements to assess clear nail plate growth and rates of clinical improvement. Clinical improvement will be assessed using the NaPSI, an objective validated measuring tool developed by one of the leaders in the field of nail pathology for use in clinical trials on treatment of nail psoriasis.

Adverse effect intensity will be assessed at each of the treatment visits using a 0-3 scale (0=none, 1=mild, 2=moderate, 3=severe) for each side effect with changes from baseline analyzed using the Wilcoxon signed-ranks test and presented as medians and ranges.

Statistical analysis will be performed using SAS version 9.2 (SAS Institute, Cary, NC). Two-tailed $P < 0.05$ will be considered statistically significant.

MONITORING AND QUALITY ASSURANCE

Site Monitoring

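### The efficacy and analysis text compares outcomes only with baseline and names no primary measure, efficacy test or rule for lowest effective, so the primary objective has no defined answer

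*Combined protocol and SAP*

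**What the plan says.** **Objective and endpoint.** Objectives makes the lowest effective concentration the primary aim. Efficacy Evaluations then states: "The primary endpoint of this study is to assess the lowest effective concentration of intralesional triamcinolone acetonide in the treatment of nail psoriasis". That repeats the aim and is not a measured variable.

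**Comparator in the efficacy and analysis text.** On clear nail growth, Efficacy Evaluations says: "This growth will be compared to the initial amount of clear nail recorded at baseline". On the other two measures: "Changes in clear area and NaPSI will also be reviewed as study intervention progresses and compared to baseline values". Data Analysis adds no further comparator: "Efficacy will be evaluated using nail plate measurements to assess clear nail plate growth and rates of clinical improvement". It assesses clinical improvement by NaPSI but gives no cut-off for an improved nail and no analysis time point.

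**Tests.** The one named test, Wilcoxon signed-ranks, is for adverse effect intensity. A general rule follows, with no provision for multiple comparisons: "Two-tailed $P < 0.05$ will be considered statistically significant".

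**Placebo elsewhere.** The Introduction gives each participant a placebo nail, "thus establishing the efficacy of ITA in our study by allowing us to compare placebo to ITA", and expects concentrations to be compared within a patient. A secondary objective is to show that the drug is "effective in the treatment of nail psoriasis when compared to placebo, using the Nail Psoriasis Severity Index as a measure of improvement". It concerns the drug as a whole, not each concentration.

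**The concern.** A lowest effective concentration can be identified only if the plan says what effective means, on which measure, against what, at what time, and which pattern of results over four concentrations gives which answer. None of this is stated. The one comparison that the efficacy text does describe, with baseline, cannot separate drug effect from change that would have happened anyway.

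The unstated choices matter. An analyst who tests change from baseline, one who tests each concentration against placebo, and one who also requires all higher concentrations to succeed can name different concentrations from the same data. The plan also does not say how several nails from one participant are to be analysed. With 10 participants, choices made after the data are seen could decide the result.

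**Working it through.** The plan gives no power, effect size, SD or correlation, so its sample size cannot be reproduced. The figures below are illustrations.

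**Inputs from the documents.** 10 participants (Study Design); up to 50 nails in five groups of about equal size, so 10 nails per group (Enrollment and Randomization); two-sided 0.05 (Data Analysis).

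**Assumptions.** Normal outcomes with total SD 1; correlation rho between nails of one participant, 0.5 with a range of 0.3 to 0.7; one nail per group per participant. No baseline covariate was simulated.

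**1. Change from baseline used as the test, with no drug effect.** A one-sample t test on 10 changes has 9 df and critical value 2.262. If all nails improve by m SD of change, the noncentrality is m × √10, and the chance of calling a given concentration effective is P(t > 2.262).

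| m | Noncentrality | Called effective |
|---|---|---|
| 0.25 | 0.79 | 11% |
| 0.5 | 1.58 | 29% |
| 0.75 | 2.37 | 56% |
| 1 | 3.16 | 80% |

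Against placebo the shared improvement cancels, and the rate favouring drug is 2.5% per concentration whatever m is.

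**2. Four unadjusted tests against placebo, nothing working.** Participant-blocked analysis: residual df = 50 − 1 − 9 − 4 = 36, critical value 2.028. By simulation (100,000 runs), any false positive is about 15%, and any favouring drug about 7.6%.

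**3. The decision rule changes the answer.** All four concentrations are set to work at 1 SD and tested unadjusted against placebo. One rule takes the lowest significant concentration; the other takes the lowest for which all higher ones are also significant. They disagree in 36%, 23% and 5% of trials at rho 0.3, 0.5 and 0.7. Both name a concentration and differ in 16%, 12% and 3%; in the rest the stricter rule names none.

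**4. Power for the lowest concentration, five nails each, all four working at 1 SD, rho 0.5.** SE of a difference = √(2 × (1 − 0.5)/10) = 0.316; noncentrality = 1/0.316 = 3.16.
- Unadjusted: P(t > 2.028) = 87% (74% to 98% over rho 0.3 to 0.7).
- Dunnett: P(t > 2.555) = 73%.
- Fixed order from the highest concentration down, each at 0.05: reaches the lowest in 68% (simulation).
- Ignoring participant, unadjusted: 59% (simulation).

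When nothing works, the chance of any claim favouring drug is about 2.5% with Dunnett and about 2.5% with fixed order.

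**5. Dependence on nails per participant.** With ten nails each (two per group), SE = √(2 × 0.5/20) = 0.224, noncentrality 4.47, df = 100 − 1 − 9 − 4 = 86, and unadjusted power is 99%. With four, three or two nails each and one placebo nail per participant, simulated unadjusted power averaged over the concentrations is 77%, 63% and 34%.

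**6. Placebo nails in the allocation table.** Group 5 stands at nails 1, 7, 13, 19, 21, 30, 35, 36, 45 and 47. Taken in order:
- Two nails each (nails 1–20): participants 1, 4, 7 and 10 get placebo; 6 of 10 do not.
- Three each (1–30): participants 1, 3, 5, 7 and 10 do (7 has two); 5 do not.
- Four each (1–40): participants 1, 2, 4, 5, 6, 8 and 9 do (9 has two); 3 do not.
- Five each: all do.

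**7. Baseline clear nail.** Efficacy Evaluations uses an amount recorded at baseline. The first-visit list under Procedures has NaPSI and photographs but no clear-nail measurement; that first appears in the list for later visits.

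**The case against.** The strongest reply is that the trial is placebo controlled and says so: the Introduction gives the purpose of the placebo nail, and a secondary objective names both comparator and measure. Comparing with baseline may only define a change score, to be set against placebo later, and the efficacy text calls the clear-growth assessment preliminary. This much stands. A reader might infer that the plan has no placebo comparison, or that followed as written it will credit spontaneous improvement to the drug. The documents support neither. They state the comparison but give it no analysis, and they do not say that significance against baseline means effective. The 11% to 80% therefore applies only if baseline change is used that way. The reply does not fill the gap: the stated placebo comparison is secondary, is for the drug overall, and has no test or time point, so it cannot identify a lowest concentration.

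Three further readings go too far.
- Five nails each is the table's planning assumption, not a best case. Inclusion sets a minimum of two nails and no maximum.
- The table taken in order breaks the one-placebo-nail rule when participants have few nails, but Enrollment and Randomization says the table will be adjusted if nail numbers differ. The text needs reconciling; it does not show that participants will lack placebo.
- The clear-nail baseline may be readable from the pre-treatment photographs, so this is an omission from a schedule list, not proof of missing data.

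One could also say that a 10-participant study needs less detail. But it sets a significance level and aims at one specific answer, and small numbers give later choices more influence.

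**Conclusion.** The concern holds in this form: the efficacy and analysis sections describe comparison with baseline only, the placebo and within-patient comparisons intended elsewhere have no analysis, and no primary measure, efficacy test or decision rule is given. This rests on reading the text and on no assumption. It must be fixed, because the primary objective cannot be answered as planned.

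The sizes are conditional. The false-claim rates for baseline change rest on the assumed shared improvement; the 15% and 7.6% rest on four unadjusted placebo tests with five nails each; the power figures rest on an assumed 1 SD effect and rho. The 2.5% under adjustment was checked for five nails each, not for sparser allocations with one placebo nail per participant.

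**What to change.** In Data Analysis:

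1. Name one primary measure at the 24-week visit. Per-nail NaPSI (0–8, Appendix A) is on both the first-visit and follow-up lists. The choice is the sponsor's, but clear growth would need a first-visit measurement added to the schedule.
2. Compare each concentration with placebo in a model with group (five levels), the nail's baseline value and a participant effect, for example a linear mixed model with Kenward-Roger degrees of freedom.
3. Control the four comparisons by one pre-stated method and write its rule. With Dunnett, lowest effective is the lowest concentration significant in favour of drug after adjustment. With fixed order from the highest down, each at two-sided 0.05 and stopping at the first failure, it is the last concentration to pass; this assumes higher concentrations work at least as well. Other methods would serve if stated in advance.
4. Report change from baseline and the other measures as supportive, with a stated improvement threshold.
5. Separately, reconcile the one-placebo-nail rule and the statement that the table will be adjusted with the allocation table itself.

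**Cost.** Wording and a few lines of SAS, with no extra participants and no extra data if NaPSI is primary. Power for the lowest concentration falls as shown in step 4 of the check (87% to 73% or 68%). It is lower with fewer nails and higher with more, and a non-significant result from few nails would not show that a concentration is ineffective.

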Another secondary objective is to determine the rate and nature of side effects experienced by patients using different concentrations of intralesional triamcinolone acetonide for the treatment of nail psoriasis.

Another secondary objective is to assess baseline quality of life in patients with nail psoriasis and determine if there is a change in quality of life with the study intervention.

SUBJECT POPULATION

Inclusion Criteria:

The subject must meet ALL the criteria listed below for entry:

1. Subject must be at least 18 years of age, of either sex or transgendered individuals, and of any race;
2. Subject must have nail psoriasis that is clinically diagnosed of at least 2 fingernails.
3. Subject must be willing to give written informed consent and able to adhere to procedures and visit schedules;
4. Subject must consent to having the fingernails photographed during the study period

Exclusion Criteria:

The subject will be excluded from entry if ANY of the criteria listed below are met:

1. Subject with any clinically significant condition or situation, other than the condition being studied that, in the opinion of the investigator, would interfere with study evaluations or optimal participation in the study. This is including, but not limited to: immunodeficiency, onychomycosis, any other nail condition other than psoriasis, allergy to triamcinolone acetonide, local anesthetic, normal saline, or any other material used for procedures.
2. Subject who has received radiation therapy, chemotherapy, and/or immunosuppressive drugs within 6 months of study, and/or oral corticosteroids for >1 month within the 6 months of study (exception: inhaled steroids);
3. Subject known to have received treatment with investigational drugs or devices within 30 days prior to enrollment into this study;
4. Subject who is unwilling to abstain from any cosmetic nail treatments outside those provided by the study clinic, beyond basic nail trimming (i.e. no spa nail treatments, no nail polish use, no other topical prescription nail medication);

5. Subject who is unwilling to abstain from any medical nail treatments on their nails other than the study intervention (i.e. topical steroids, antifungal creams) for the duration of the study intervention and for duration of the washout period (if applicable);
6. Subject who is part of the staff personnel directly involved with this study or a family member of the investigational study staff

CONCOMITANT MEDICATIONS

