Washout Period: Subjects who are using any form of treatment on their nails at the time of the screening visit may participate in the study provided that they are willing to undergo a two-month washout period. During this time, they must abstain from using any nail treatments (including, but not limited to: spa nail treatments, nail polish use, prescribed topical or systemic medications indicated for the nails, over the counter nail treatments, or any other nail intervention with the exception of routine clipping and washing.) After the washout period, the subject may be re-evaluated for participation in the study.

Enrollment and Randomization: Patients with at least two affected fingernails will be enrolled. For each participant, one fingernail will receive an intralesional injection of 0.1-0.2 mL of normal saline (placebo). The other affected fingernail(s) will receive an injection of 0.1-0.2mL of a pre-determined concentration of ITA. Four concentrations of ITA will correspond to four study groups: 2.5mg/mL, 5mg/mL, 7.5mg/mL and 10mg/mL. Participants' fingernails will be randomized such that there are approximately equal numbers of fingernails in each of the five groups (four study interventions, one placebo). To avoid bias, fingernails will be assigned to groups systematically. Fingernails will be assigned to groups in order of anatomical convention. For example, if the subject has involvement of both the thumb, forefinger and third finger of the right hand, the thumb is the first digit, so, if involved, it will be assigned first according to the table below. If a subject has involvement of fingernails of both the right and left hand, the fingernails of the right hand will be assigned before the left. The table assumes that up to 50 nails will be affected between the 10 subjects enrolled. In our clinical experience, this is a reasonable expectation. If more or fewer fingernails are involved during the enrollment period, the randomization table will be adjusted accordingly. The concentration of ITA injected will be different for each group. All other study procedures will be the same between groups.

Fingernail	Group
1	5
2	3
3	4
4	1
5	2
6	4
7	5
8	1
9	3
10	2
11	3
12	4
13	5
14	1
15	2

16	2
17	1
18	3
19	5
20	4
21	5
22	4
23	3
24	2
25	1
26	1
27	2
28	3
29	4
30	5
31	1
32	2
33	4
34	3
35	5
36	5
37	3
38	4
39	2
40	1
41	1
42	3
43	4
44	2
45	5
46	1
47	5
48	2
49	4
50	3

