APPENDIX A

Nail Psoriasis Severity Index

Nail Psoriasis Severity Index (NAPSI)

The target nail is graded for nail matrix psoriasis and nail bed psoriasis. The sum of these two scores is the total score for that nail.

Nail Matrix Psoriasis consists of any the following: pitting, leukonychia, red spots in the lunula, and nail plate crumbling.

Score for **matrix psoriasis** 2

- 0=none
- 1=present in 1/4 nail
- 2=present in 2/4
- 3=present in 3/4
- 4=present in 4/4

Nail Bed Psoriasis is the presence or absence of any of the following: onycholysis, splinter hemorrhages, oil drop (salmon patch) discoloration, and nail bed hyperkeratosis.

Score for **nail bed psoriasis** 3

- 0=none
- 1=present in 1/4 nail
- 2=present in 2/4
- 3=present in 3/4
- 4=present in 4/4

Total for nail 5 (0-8)

C

From Rich, P. and R.K. Scher, *Nail Psoriasis Severity Index: a useful tool for evaluation of nail psoriasis*. J Am Acad Dermatol, 2003. **49**(2): p. 206-12.

Table I . Instructions for grading psoriatic nails using NAPSI*

The nail is divided with imaginary horizontal and longitudinal lines into quadrants. Each nail is given a score for nail bed psoriasis (0-4) and nail matrix psoriasis (0-4) depending on the presence of *any* of the features of nail psoriasis in that quadrant.

1. Evaluation 1: Nail matrix. In each quadrant of the nail, nail matrix psoriasis is evaluated by presence of *any* of the nail matrix features (pitting, leukonychia red spots in the lunula, crumbling): 0 for none, 1 if present in 1 quadrant of the nail, 2 if present in 2 quadrants of the nail, 3 if present in 3 quadrants of the nail, and 4 if present in 4 quadrants of the nail.
2. Evaluation 2: Nail bed. Nail bed psoriasis is evaluated by the presence of *any* of the nail bed features (onycholysis, splinter hemorrhages, subungual hyperkeratosis, "oil drop" (salmon patch dyschroma): 0 for none, 1 for 1 quadrant only, 2 for 2 quadrants, 3 for 3 quadrants, and 4 for 4 quadrants.
3. Each nail gets a matrix score and a nail bed score, the total of which is the score for that nail (0-8).
4. Each nail is evaluated, and the sum of all the nails is the total NAPSI score. The sum of the scores from all nails is 0-80; or 0-160 if toenails are included. At any time the matrix or nail bed score can be assessed independently if desired.

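### The NaPSI efficacy analysis is left as undefined improvement rates and comparison with baseline; the week-24 per-nail score should be analysed with that nail's baseline NaPSI as covariate

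*Combined protocol and SAP*

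**What the plan says.** Two sentences cover the use of NaPSI for efficacy. Data Analysis states: "Efficacy will be evaluated using nail plate measurements to assess clear nail plate growth and rates of clinical improvement". The sentence after it makes NaPSI the measure of clinical improvement. Efficacy Evaluations adds: "Changes in clear area and NaPSI will also be reviewed as study intervention progresses and compared to baseline values". Neither section gives a responder threshold, says whether a rate is a proportion or a speed, or names a test, model or covariate for NaPSI. The only named test, the Wilcoxon signed-ranks test, is for adverse-effect intensity. The significance rule is general: "Two-tailed $P < 0.05$ will be considered statistically significant".

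Appendix A scores every nail from 0 to 8. The visit lists under Research Design / Methods have NaPSI completed at the first visit, at each later treatment visit and at the 24-week follow-up, so a baseline and a final score exist for every nail. Entry requires only this: "Subject must have nail psoriasis that is clinically diagnosed of at least 2 fingernails". No minimum NaPSI is set.

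**The concern.** The secondary objective of showing efficacy against placebo names NaPSI as its measure, and the primary objective (lowest effective concentration) depends on comparing groups that hold about 10 nails each. At that size the way the score is summarised matters a good deal.

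A nail that starts at 1 can improve by only 1 point, while a nail that starts at 8 can improve by 8. A rate of any improvement treats 8 to 7 the same as 8 to 0, and counts a one-point fluctuation in a saline nail as a success. A raw change score uses the whole scale, but it carries part of any chance difference in starting severity into the comparison of concentrations. The plan already collects the variable that would deal with this and does not say it will be used. With the threshold and the model both open, they could also be chosen after the data are seen.

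**Working it through.** **Inputs from the documents.** Two-sided 0.05 (Data Analysis); 10 participants; up to 50 nails in five groups (Research Design / Methods); per-nail score 0-8 (Appendix A).

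**Assumptions, because the documents give no figures.** Correlation ρ between baseline and week-24 score 0.3 to 0.7; SD 2 points; correlation between nails of one participant 0.4; the effect sizes stated below.

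**1. The plan's own figure.** There is no power or sample-size calculation to reproduce. The allocation table has 50 entries, 10 for each of groups 1 to 5, and every consecutive block of five contains each group once. Ten nails per group is therefore the planning figure, subject to 50 being an upper expectation.

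**2. Change score against baseline-adjusted score.** With equal variance σ² at both times, the variance per nail is 2σ²(1 − ρ) for change and σ²(1 − ρ²) for the adjusted score. The information kept by the change score is (1 − ρ²) / [2(1 − ρ)] = (1 + ρ)/2.

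**3. Splitting the change into improved or not.** The information kept relative to the change itself is φ(z_p)² / [p(1 − p)], where p is the proportion of responders. At p = 0.5 this is 0.637; at p = 0.2 it is 0.490. Multiplying by step 2 gives the comparison with the adjusted score:

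| Information kept | ρ = 0.3 | ρ = 0.5 | ρ = 0.7 |
|---|---|---|---|
| Raw change, (1 + ρ)/2 | 65% | 75% | 85% |
| Responder rate, p = 0.5 | 0.637 × 0.65 = 41% | 0.637 × 0.75 = 48% | 0.637 × 0.85 = 54% |
| Responder rate, p = 0.2 | 0.490 × 0.65 = 32% | 0.490 × 0.75 = 37% | 0.490 × 0.85 = 42% |

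With half the nails responding, a responder rate loses more than half the information only when ρ is below 2 × 0.5/0.637 − 1 = 0.57.

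**4. Chance baseline differences, two groups of 10 nails, SD 2.**
- Independent nails: SE = 2 × √(2/10) = 0.89 point.
- Nails paired within participants, correlation 0.4: SE = 2 × √(2 × 0.6/10) = 0.69 point; about 0.66 after rounding and clipping to the scale.

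On the unclipped scale a change-score comparison carries a fraction (1 − ρ) of the baseline difference, that is 0.7 to 0.3 of it. A one-SE difference of 0.69 point therefore moves the comparison by 0.69 × 0.7 = 0.48 point at ρ = 0.3 and 0.69 × 0.3 = 0.21 point at ρ = 0.7.

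**5. Check on simulated integer scores, independent nails, 10 per group.** Baseline mean 5, SD 2, true difference 2.5 points, responder defined as at least 50% improvement:

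| Power | ρ = 0.3 | ρ = 0.5 | ρ = 0.7 |
|---|---|---|---|
| Baseline-adjusted score | 75% | 83% | 93% |
| Raw change | 59% | 73% | 90% |
| Responder rate, uncorrected chi-square | 56% | 64% | 76% |
| Responder rate, Fisher exact | 37% | 45% | 58% |

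Under no difference, type I error was about 5% for the two score analyses, 1.2-2.8% for chi-square and 0.2-0.5% for Fisher. Part of the responder-rate deficit is therefore due to conservative testing.

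**6. One model on all nails.** This simulation used 50 nails, unequal numbers of nails per participant, participant effects, a true difference of 2 points, SD 2 and within-participant correlation 0.4. Adding first-visit NaPSI raised power over the raw change score from 56 to 76%, 67 to 81% and 86 to 91% at ρ = 0.3, 0.5 and 0.7. Type I error was 4.4-5.6%.

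**The case against.** The strongest reply is that the plan is silent rather than wrong. It sets no cut-off, a rate might mean a speed, and the sentence on changes from baseline may describe monitoring during treatment. Baseline adjustment is neither planned nor excluded. This stands: a reader might infer that the protocol prescribes an unadjusted responder analysis, and the documents do not say so. What they support is that the analysis is undefined, that the measures they mention are weaker than one already available, and that the baseline score has no stated role beyond comparison.

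Three other stronger readings also fail.
- That most of the information is lost whatever is done. This applies to a responder rate over much of the assumed range, but not to a change score, which loses 15-35%.
- That a responder analysis would have almost no power. With 10 pairs and a 2-point difference, exact McNemar on any improvement gives only about 7/11/20% at ρ = 0.3/0.5/0.7. Its type I error at ρ = 0.5 is about 0.3%, and the mid-p version raises power to 19/25/38%. The protocol names neither test.
- That baseline imbalance biases the result. Provided the allocation list is unrelated to severity, imbalance adds variance that the standard error already reflects.

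A further objection is that ten within-participant pairs per concentration are not assured, since two affected nails suffice for entry and 50 nails is an upper figure. With only 5 or 6 pairs at ρ = 0.5, regressing each pair separately gives no gain: 29/40% adjusted against 32/40% for change. That counts against separate pairwise regressions. It does not count against a single model on all nails, which kept its gain with unequal nail counts (step 6).

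**Conclusion.** The point holds in a limited form. The NaPSI efficacy analysis has no threshold, test or model, and no adjustment is planned for a baseline score that is collected for every nail and may differ widely because entry sets no minimum. Relative to the baseline-adjusted week-24 score, a responder rate would keep about 32-54% of the information and a raw change score 65-85%. Chance baseline differences of about 0.7 point (paired nails) to 0.9 point (independent nails) per standard error would add noise, not systematic error.

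The percentages come from normal-theory formulas, and SD, effect size and correlations are assumptions. The adjusted score had the highest power at every correlation examined, but its advantage over the change score narrows as the correlation rises. The plan should be changed; this is not a flaw that invalidates the trial.

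**What to change.** In Data Analysis, define the NaPSI efficacy analysis as one model of the week-24 per-nail score (0-8) on all study nails, with treatment group (four concentrations and saline), that nail's first-visit NaPSI as covariate, and a participant effect. Report adjusted differences of each concentration from saline, and between concentrations, with 95% confidence intervals. Keep improvement rates as a descriptive table with the threshold stated in advance.

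The cost is a few sentences and one degree of freedom. It needs no new visit, measurement or participant. The gain over a change score is small if the baseline-to-final correlation is near 0.7.
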